Appendix 2 List of Permitted and Prohibited Prior/Concomitant Medications

Prohibited medications are shown in [Listing 1](#) through [Listing 5](#). Medications permitted with restrictions are listed in [Listing 6 through Listing 8](#). (revised per Amendment 04) **These may not be all-inclusive listings.** Please contact the medical monitor(s) if the investigators have any questions or concerns regarding any medication not listed that your subjects may be taking before enrollment or start during the course of the E2609-G000-202 study.

Antibiotics, analgesics, and anti-inflammatory drugs intended for short courses of treatment are permitted and do not need to follow the restrictions of [Listing 8](#) for a stable dose of 4 weeks before Baseline. If these medications may affect cognitive function but the medications are clinically indicated, then cognitive testing should not take place until at least 72 hours after the last dose of the course of treatment.

Prohibited Prior/Concomitant Medications

Listing 1 Drugs with High Risk of Torsades de Pointes or QTc Prolongation

| Generic name | Brand name (Names shown are not exhaustive and are examples only; names may be the ® or ™) | Comments |
|---|--|---|
| Prohibited from 14 days (or 5 half-lives, whichever is longer) before Randomization until after the last treatment visit | | |
| Anti-arrhythmic/ abnormal heart rhythm | | |
| Amiodarone | Cordarone; Pacerone | Incidence in females greater than males, Torsades de Pointes risk regarded as low |
| Disopyramide | Norpace | Incidence in females greater than males |
| Dofetilide | Tikosyn | |
| Ibutilide | Corvert | Incidence in females greater than males |
| Procainamide | Pronestyl; Procan | |
| Quinidine | Cardioquin; Quinaglute | Incidence in females greater than males |
| Sotalol | Betapace | Incidence in females greater than males |
| Antihistamine/ allergic rhinitis | | |
| Astemizole | Hismanal | No longer available in United States |
| Terfenadine | Seldane | No longer available in United States |
| Anti-anginal/ heart pain | | |
| Bepridil | Vascor | Incidence in females greater than males |
| Antibiotic/ bacterial infection | | |
| Clarithromycin | Biaxin | |
| Moxifloxacin | Avelox | |
| Sparfloxacin | Zagam | |
| Listing 1 continued | | |
| Antimalarial/ malaria infection | | |
| Chloroquine | Aralen | |
| Halofantrine | Halfan | Incidence in females greater than males |
| Antipsychotic/ anti-emetic/ schizophrenia/ nausea | | |

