| Chlorpromazine | Thorazine | |
| Gastrointestinal stimulant/ heartburn | | |
| Cisapride | Propulsid | |

Listing 1 Drugs with High Risk of Torsades de Pointes or QTc Prolongation

| Generic name | Brand name (Names shown are not exhaustive and are examples only; names may be the ® or ™) | Comments |
|--|--|---|
| Antinausea/ nausea | | |
| Domperidone | Motillum | Not available in the United States |
| Sedative; antinausea/ anesthesia adjunct, nausea | | |
| Droperidol | Inapsine | |
| Antibiotic; gastrointestinal stimulant/ bacterial infection; increase gastrointestinal motility | | |
| Erythromycin | Erythrocin; E.E.S. | Incidence in females greater than males |
| Antipsychotic/ schizophrenia | | |
| Haloperidol | Haldol | When given intravenously or at higher than recommended doses, risk of sudden death, QT prolongation, and torsades increases |
| Mesoridazine | Serentil | |
| Thioridazine | Mellaril | |
| Opiate agonist/ pain control, narcotic dependence | | |
| Levomethadyl | Orlaam | |
| Methadone | Methadose; Dolophine | Incidence in females greater than males |
| Anti-infective/ pneumocystis pneumonia | | |
| Pentamidine | Pentam; NebuPent | Incidence in females greater than males |
| Antipsychotic/ Tourette's ties | | |
| Pimozide | Orap | Incidence in females greater than males |
| Antilipemic/ hypercholesterolemia | | |
| Probucol | Lorelco | No longer available in United States |
| Anticancer | | |
| Arsenic trioxide | Trisenox | Used for leukemia |
| Vandetanib | Zactima | Used for thyroid cancer |

Note: This list is not exhaustive.

QTc = Corrected QT interval.

Listing 2 Prohibited Medications Within 5 Half-lives or 60 days, Whichever is Longer, Before Randomization and Until after the Last Treatment Visit

| Generic name | Brand name (Names shown are not exhaustive and are examples only; names may be the ® or ™) |
|---|--|
| Systemic Immunosuppressants^{a,b} and Immunomodulatory therapy | |
| Azathioprine | Azasan, Imur |
| Ciclosporine | Gengraf, Neoral |
| Dexamethasone | Decadron, Dexasone, Diodex, Hexadrol, Maxidex |
| Fingolimod | Gilenya |
| Methotrexate | Trexall |
| Methylprednisolone | Medrol, Meprolone |
| Mycophenolate | CellCept, Myfortic |
| Prednisolone | Deltasone, Prednicot, Prednisone Intensol, Rayos, Sterapred, Sterapred DS |

Note: This list is not exhaustive.

- a: Topical and inhaled formulations with minimal systemic exposure need not be prohibited.

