| Midazolam | Versed |
| Olanzapine | Zyprexa |
| Promethazine | Phenergan; others |
| Ramelteon | Rozerem |
| Risperidone | Risperdal |
| Temazepam | Restoril |
| Triazolam | Halcion |
| Zolpidem | Ambien; others |
| Zopiclone | (various) |
| Other benzodiazepines, tricyclic antidepressants, antipsychotics and other drugs which are used on PRN basis as sedatives | |

Note: This list is not exhaustive

**Listing 7 Permitted Medications Used on PRN Basis Which are Not to be Used
Within 72 Hours before Cognitive Testing**

| Generic name | Brand name (Names shown are not exhaustive and are examples only; names may be the [®] or [™]) |
|--------------|--|
|--------------|--|

PRN = Pro re nata

Listing 8 Permitted Centrally Active or Psychiatric Medications

| Generic Name | Brand name (Names shown are not exhaustive and are examples only; names may be the ® or ™) |
|--|--|
| 
If to be used on a PRN basis see Listing 7. If to be used chronically, subjects must be on a stable dose for ≥4 weeks before Baseline. Changes in dose or initiation of new concomitant medications for chronic use (not PRN use) is permitted but if the medication affects cognitive function, do not conduct cognitive testing until the dose is stable for 4 weeks.
 | |
| Antidepressants | |
| Amitriptyline hydrochloride | Elavil |
| Amoxapine | Amoxapine |
| Bupropion | Aplenzin, Budeprion, Buproban, Zyban, Wellbutrin |
| Citalopram | Celexa |
| Clomipramine hydrochloride | Anafranil |
| Desipramine hydrochloride | Norpramin |
| Desvenlafaxine | Pristiq |
| Doxepin hydrochloride | Prudoxin, Silenor, Sinequan, Zonalon |
| Duloxetine | Cymbalta |
| Escitalopram | Lexapro |
| Fluoxetine | Prozac, Sarafem, Selfemra |
| Fluvoxamine | Luvox |
| Imipramine hydrochloride | Tofranil |
| Isocarboxazid | Marplan |
| Maprotiline hydrochloride | Ludiomil |
| Mirtazapine | Remeron Soltab |
| Nortriptyline hydrochloride | Aventyl, Pamelor |
| Paroxetine | Paxil, Pexeva |
| Phenelzine | Nardil |
| Protriptyline hydrochloride | Vivactil |
| Rasagiline | Azilect |
| Selegiline | EMSAM |
| Sertraline | Sertaraline, Zoloft |
| Tranlycypromine | Parnate |
| Trazodone hydrochloride | Desyrel, Oleptro |
| Trimipramine maleate | Surmontil |
| Venlafaxine hydrochloride | Effexor |

Listing 8 Permitted Centrally Active or Psychiatric Medications

| Generic Name | Brand name (Names shown are not exhaustive and are examples only; names may be the ® or ™) |
|---|--|
| Mood Stabilizers (Listing 8 continued) | |

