| Carbamazepine | Carbatrol, Epitol, Equetro, Tegretol, Tegretol XR |
| Lamotrigine | Lamictal, Lamictal CD, Lamictal ODT, Lamictal XR |
| Valproic acid | Depacon, Depakene, Depakote, Depakote ER, Divalproex Sodium, Stavzor, Valproate |
| Antipsychotics | |
| Acetophenazine | Tindal |
| Aripiprazole | Abilify |
| Asenapine | Saphris |
| Olanzapine | Zyprexa |
| Chlorpromazine | Thorazine |
| Haloperidol | Haloperidol, Haldol |
| Clozapine | Clozaril, Fazacllo |
| Fluphenazine | Prolixin |
| L-Methylfolate | Deplin, L-Methylfolate Calcium |
| Loxapine | Loxitane |
| Mesoridazine | Serentil |
| Perphenazine | Trilafon |
| Quetiapine | Seroquel |
| Risperidone | Risperdal |
| Thioridazine | Mellaril |
| Thiothixene | Navane |
| Trifluoperazine | Stelazine |
| Benzodiazepines | |
| Alprazolam | Alprazolam Intensol, Niravam, Xanax |
| Chlordiazepoxide | H-Tran, Librium |
| Clonazepam | Ceberclon, Klonopin |
| Diazepam | Diastat, Dizac, Valium |
| Estazolam | ProSom |

Listing 8 Permitted Centrally Active or Psychiatric Medications

| Generic Name | Brand name (Names shown are not exhaustive and are examples only; names may be the ® or ™) |
|---------------|--|
| Flunitrazepam | Rohypnol |
| Flurazepam | Dalmane |
| Lorazepam | Ativan |
| Midazolam | Versed |
| Temazepam | Restoril |
| Triazolam | Halcion |
| Zopiclone | Imovane, Zimovane |
| Zopidem | Ambien, Ambien CR, Intermezzo, Stilnox, Stilnoct, Sublinox, Hypnogen, Zolsana |

Note: This list is not exhaustive.

PRN = Pro re nata

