9.4.7 Prior and Concomitant Therapy

Medication (including over-the-counter medications) or therapy administered to the subject before the study (within 6 months of randomization) and during the study (starting at the date of informed consent) will be recorded on the Prior & Concomitant Medication eCRF or Non-Pharmacological Procedures eCRF. The investigator will record on the Adverse Event eCRF any AE for which the concomitant medication/therapy was administered. If the concomitant medication/therapy is being administered for a medical condition present at the time of entry into the study, the investigator will record the medical condition on the Medical History and Current Medical Condition eCRF.

Listings of prohibited and permitted drugs are provided in [Appendix 2](#). Prohibited medications are presented in [Listing 1](#) through [Listing 5](#). Medications that are permitted with restrictions are listed in [6](#) through [Listing 8](#). (revised per Amendment 04)

The following agents are not permitted before randomization (specific timeframes are shown below) and throughout the study until after the last treatment visit: (revised per Amendment 04)

- Drugs which may cause QTc prolongation are not permitted for a period of 5 half-lives or 14 days (whichever is longer) before randomization
- Strong CYP3A4 inhibitors are not permitted for a period of 5 half-lives or 14 days (whichever is longer) before randomization
- Live vaccines are not permitted within 3 months before randomization. This does not apply to non-live/inactivated vaccines
- Ig therapy and biologic drugs are not permitted within 6 months before randomization

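### Appendix 2 both prohibits and permits the same four QTc-prolonging antipsychotics, and does not say which listing governs

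*Protocol*

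**What the plan says.** Appendix 2 of the protocol opens by sorting its listings into two groups: 1 to 5 are prohibited, and 6 to 8 are permitted with restrictions. Sites are asked to contact the medical monitor "if the investigators have any questions or concerns regarding any medication not listed".

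**Listing 1** covers drugs with high torsades or QTc risk. Its rule is "Prohibited from 14 days (or 5 half-lives, whichever is longer) before Randomization until after the last treatment visit". Its rows include "Chlorpromazine | Thorazine" and "Haloperidol | Haldol | When given intravenously or at higher than recommended doses, risk of sudden death", and it also names mesoridazine and thioridazine.

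**Listing 8** covers permitted centrally active or psychiatric drugs. Chronic use is allowed if the dose has been steady for four weeks or more ahead of Baseline. On study, "Changes in dose or initiation of new concomitant medications for chronic use (not PRN use) is permitted", subject only to a delay in cognitive testing if the drug affects cognition. Its antipsychotic block includes "Haloperidol | Haloperidol, Haldol", and also chlorpromazine, mesoridazine and thioridazine.

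**Listing 7** covers as-needed drugs and ends with an open line: "Other benzodiazepines, tricyclic antidepressants, antipsychotics and other drugs which are used on PRN basis as sedatives". It states no exception for Listing 1.

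**Section 9.4.7** says "Drugs which may cause QTc prolongation are not permitted for a period of 5 half-lives or 14 days" and extends the bar through the treatment period. The same section points to Listings 6 to 8 for what is permitted with restrictions.

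**The concern.** One appendix gives two opposite instructions for the same named drugs. A coordinator who looks up haloperidol under antipsychotics in Listing 8 finds express permission, including permission to start it during treatment. Nothing at that point refers back to Listing 1.

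Three things are at stake:

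- **Subject safety.** The subject may receive a drug that the protocol itself classes as high risk for torsades or QTc prolongation, on top of a study drug whose QT effect is being watched. Section 7.1 reports a QTcF rise of 14.9 msec at a single 800 mg dose. That is 800/50 = 16 times the top dose here, so it explains why the restriction exists. It does not predict the effect at 50 mg.
- **Avoidable loss of treatment.** Section 9.3.3, items g and h, requires discontinuation of study drug for an average QTcF above 500 msec, or for a rise above 60 msec with QTcF above 450 msec.
- **Noise in the primary safety data.** ECG parameters are part of the primary endpoint, and each arm has about 15 subjects. One QTcF outlier caused by a concomitant drug would be 1/15, or about 7%, of an arm.

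**Working it through.** There is no planned figure to reproduce. The check is a name-by-name comparison of the listings, a search for any rule that ranks them, and a reading of the ECG schedule.

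**1. Name overlap.** All generic names in Listings 1, 5, 7 and 8 were transcribed and intersected.

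- Listing 1 names 30 drugs. Five stand under antipsychotic headings: chlorpromazine, haloperidol, mesoridazine, thioridazine and pimozide.
- Listing 8 has 17 entries under antipsychotics.
- Listing 1 and Listing 8 share chlorpromazine, haloperidol, mesoridazine and thioridazine: 4 drugs.
- Listing 1 and Listing 7 (named drugs) share none. Listing 5 shares none with Listing 7 or Listing 8.

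So 4 of 5 prohibited antipsychotics (80%) reappear as permitted, and only pimozide does not. They make up 4/17 (24%) of the antipsychotic block in Listing 8 and 4/30 (13%) of Listing 1. Listing 1's remark on haloperidol says that risk increases with intravenous or high-dose use. It does not exempt oral or ordinary doses.

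**2. Is there a precedence rule?**

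| Place | What it does | Does it rank Listing 1 over Listing 8? |
|---|---|---|
| Appendix 2, introduction | Sorts listings into prohibited and permitted; refers unlisted drugs to the medical monitor | No; these four drugs are listed |
| 9.4.7, QTc bullet | Bars the class | No; the same section also points to Listings 6 to 8 as permitted |
| 9.4.7, on drugs started or adjusted on study | Allows them if not already prohibited in that section | No; it does not mention the listings |
| 9.3.2, Exclusion 25 | Excludes users of QT-prolonging drugs | No; it applies at entry only |
| 9.3.2, Exclusion 37 | Excludes breaches of the medication restrictions | No; it points back to the text in conflict |

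**3. Which version.** The file holds two complete copies of Appendix 2, one in the Amendment 06 text and one in the Amendment 05 text. The overlap is in both. Sections 9.3.2, 9.3.3 and 9.4.7 are shown only in the Amendment 05 text. The conflict does not depend on them, because it stands inside the Amendment 06 appendix alone.

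**4. ECG coverage.** Table 7 schedules on-treatment ECGs at Visits 5, 7, 9, 11, 14, 16 and 18, which are Weeks 2, 4, 8, 12, 26, 52 and 78. The gaps are 2, 4, 4, 14, 26 and 26 weeks. A drug started just after Week 26 could therefore run for up to about 26 weeks before the next scheduled ECG.

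**The case against.** The best defence is that the protocol, read as a whole, already prohibits these drugs. The synopsis bars QTc-prolonging agents for the whole study and cites Appendix 2 for the detailed list. Both the synopsis and Section 9.4.7 limit the stable-dose rule to drugs that are not prohibited. The synopsis puts the same limit on starting a drug that may affect cognition. Exclusions 25 and 37 largely close the route at entry.

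This stands as evidence of intent. It does not settle the conflict, because a permission by name can be read as a specific exception to a general class bar, and nothing says otherwise.

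Four further points are fair:

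- **Incomplete text.** The Amendment 06 body sections are not all shown, so the absence of a precedence rule can be asserted only for the text at hand.
- **The 26-week gap is a worst case.** It exists for every subject whatever the listings say. Concomitant medications are recorded at each treatment visit from Visit 4, including Weeks 39 and 65, so a new antipsychotic should be noticed within about 13 weeks. Unscheduled ECGs are possible, and Section 9.4.1 has the investigator discuss concurrent illness with the medical monitor.
- **Listing 7 is secondary.** Its open line names no Listing 1 drug.
- **No statistical quantity is affected.** Sample size, error rates and analysis sets do not change.

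**Conclusion.** The contradiction is real and should be corrected. Four named drugs are prohibited in one listing and permitted in another, and no text shown says which governs. It is an operative safety instruction stated in two opposite ways, so it goes beyond a drafting slip.

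The realistic exposure is a drug started on study by a site that consults Listing 8 alone. How often that would happen is unknown, because the documents give no usage rate for these drugs. Because assignment is randomized and blinded, any effect on between-arm QTcF comparisons would be noise or chance imbalance, not systematic confounding. The conclusion rests on the two listings as printed and does not depend on any assumed QT effect at the study doses.

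**What to change.** - Delete chlorpromazine, haloperidol, mesoridazine and thioridazine from Listing 8.
- Add one sentence to Appendix 2: Listings 1 to 5 override Listings 6 to 8, including the open class lines in Listing 7.
- Write to sites with the correction and ask them to check each subject's current concomitant medications against Listing 1.

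The cost is four deleted rows, one added sentence and a site letter. No new data, visits or analyses are needed.

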Appendix 3 Pharmacodynamic, Pharmacogenomic, and Other Biomarker Research

Subjects enrolled in this clinical study will have biologic samples collected for PD, PGx, and other biomarker analysis. These samples may be used for discovery and validation to identify biomarkers that may be used for exploratory evaluation of response or safety-related outcomes as well as for use in diagnostic development.

The PGx samples may be used to identify genetic factors that may influence a subject's exposure to the study drug, as well as genetic factors that may have an effect on clinical response or potential AEs related to study drug, and to explore the role of genetic variability in response. Samples may be analyzed to determine a subject's genotypes or sequence for a number of genes or non-coding regulatory regions. The research may include the investigation of polymorphisms in genes that are likely to influence the study drug PK or therapeutic response.

Collection of the PD, PGx, and other biomarker samples will be bound by the sample principles and processes outlined in the main study protocol. Sample collection for PD, PGx, and other biomarker analysis is required as per the study protocol unless the collection and use of the samples is prohibited by specific country laws.

Sample Collection and Handling

The samples will be collected according to the study flow chart. If, for operational or medical reasons, the genomic DNA blood sample cannot be obtained at the prespecified visit, the sample can be taken at any study center visit at the discretion of the investigator and site staff.

Security of the Samples, Use of the Samples, Retention of the Samples

Sample processing, for example DNA or RNA extraction, genotyping, sequencing, or other analysis will be performed by a laboratory under the direction of the sponsor. Processing, analysis, and storage will be performed at a secure laboratory facility to protect the validity of the data and maintain subject privacy.

Samples will only be used for the purposes described in this protocol. Laboratories contracted to perform the analysis on behalf of the sponsor will not retain rights to the samples beyond those necessary to perform the specified analysis and will not transfer or sell those samples. The sponsor will not sell the samples to a third party.

Samples will be stored for up to 15 years after the completion of the study (defined as submission of the clinical study report to the appropriate regulatory agencies). At the end of the storage period, samples will be destroyed. Samples may be stored longer if a health authority (or medicinal product approval agency) has active questions about the study. In

this special circumstance, the samples will be stored until the questions have been adequately addressed.

It is possible that future research and technological advances may identify genomic variants of interest, or allow alternative types of genomic analysis not foreseen at this time. Because it is not possible to prospectively define every avenue of future testing, all samples collected will be single or double coded (according to the ICH E15 guidelines) in order to maintain subject privacy.

Right to Withdraw

If, during the time the samples are stored, a participant would like to withdraw his/her consent for participation in this research, Eisai will destroy the samples. Information from any assays that have already been completed at the time of withdrawal of consent will continue to be used as necessary to protect the integrity of the research project.

Subject Privacy and Return of Data

No subject-identifying information (eg, initials, date of birth, government identifying number) will be associated with the sample. All PD and other biomarker samples will be single coded. Genomic DNA samples used to explore the effects on PK, treatment response, and safety will be single coded. Genomic DNA samples that will be stored for long-term use (defined as 15 years after the completion of the study) will be double coded. Double coding involves removing the initial code (subject ID) and replacing with another code such that the subject can be re-identified by use of 2 code keys. The code keys are usually held by different parties. The key linking the sample ID to the subject number will be maintained separately from the sample. At this point, the samples will be double-coded, the first code being the subject number. Laboratory personnel performing genetic analysis will not have access to the “key.” Clinical data collected as part of the clinical trial will be cleaned of subject identifying information and linked by use of the sample ID “key.”

The sponsor will take steps to ensure that data are protected accordingly and confidentiality is maintained as far as possible. Data from subjects enrolled in this study may be analyzed worldwide, regardless of location of collection.

The sponsor and its representatives and agents may share coded data with persons and organizations involved in the conduct or oversight of this research. These include:

- CROs retained by the sponsor
- IECs or IRBs that have responsibility for this research study
- National regulatory authorities or equivalent government agencies

At the end of the analysis, results may be presented in a final report which can include part or all of the coded data, in listing or summary format. Other publication (eg, in peer-reviewed

scientific journals) or public presentation of the study results will only include summaries of the population in the study, and no identified individual results will be disclosed.

Given the research nature of the PD, PGx, and other biomarker analysis, it will not be possible to return individual data to subjects. The results that may be generated are not currently anticipated to have clinical relevance to the patients or their family members. Therefore, these results will not be disclosed to the patients or their physicians.

If at any time, PD, PGx, or other biomarker results are obtained that may have clinical relevance, IRB review and approval will be sought to determine the most appropriate manner of disclosure and to determine whether or not validation in a Clinical Laboratory Improvement Amendments-certified setting will be required. Sharing of research data with individual patients should only occur when data have been validated by multiple studies and testing has been done in Clinical Laboratory Improvement Amendments-approved laboratories.

